# 11.5 Procedures for Post-discontinuation Follow-up

All unresolved (including improved) adverse events will be followed as described in Section 9.7.4.5.

# 12. Statistical Analysis

# 12.1 Selection of Sample Size

A precision-based sample size was selected for this exploratory study.

To allow the estimation of the incidence of CIPN in each of the ART-123 1-dose, ART-123 3-dose, and placebo groups at a precision of  $\pm 20\%$ , a target sample size of 25 per group for a total of 75 was selected.

#### 12.2 Statistical Analysis Plan

Key elements of the statistical analysis plan are presented here. The detailed aspects of statistical analysis will be stated in a statistical analysis plan to be finalized before unblinding.

# 12.3 Analysis Populations

# 12.3.1 Analysis Populations for Assessing Efficacy

The two analysis populations for assessing efficacy are defined as the full analysis set (FAS) and the per-protocol set (PPS). Decisions on whether subjects will be included in the analysis populations and the following details will comply with subject handling criteria to be established later.

# > Full analysis set (FAS)

This population consists of all subjects assigned to the investigational product except:

- Subjects with a GCP violation
- Subjects who do not receive oxaliplatin
- Subjects who do not receive the investigational product
- Subjects with no available efficacy data following investigational product administration

#### ➤ Per-protocol set (PPS)

The PPS consists of all full analysis set subjects except:

- Subjects with an inclusion/exclusion criterion violation
- Subjects with another major protocol deviation

#### 12.3.2 Analysis Population for Assessing Safety

This population consists of all subjects assigned to the investigational product except:

• Subjects who do not receive the investigational product

#### 12.3.3 Analysis Populations for Assessing Pharmacokinetics

This population consists of all subjects assigned to the investigational product except:

- Subjects with a GCP violation
- Subjects who do not receive the investigational product

#### 12.4 Handling of Data

Major rules for handling efficacy data are discussed below. Details about the following and other data-handling rules will comply with data-handling criteria to be established later.

- Handling of missing data on whether an assessment is NCI-CTCAE Grade 1 or greater
   Consider subjects for whom these data are missing to have had an NCI-CTCAE Grade 1 or
   greater event. Perform sensitivity analysis that includes analysis with a missing NCI-CTCAE
   grade for all such subjects.
- Handling of NCI-CTCAE evaluation data in the second and subsequent courses
   Evaluate the Day 1 (before infusion of investigational product or mFOLFOX6) NCI-CTCAE
   grades as those from the immediately preceding course. Evaluate the Days 2, 3, 15, and 29
   NCI-CTCAE grades as those observed within the course.
- Handling of missing efficacy endpoint data (continuous variables)
   Do not impute missing continuous efficacy endpoint data. Perform sensitivity analyses with imputation using the last-observation-carried-forward (LOCF) approach.

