#### [1] Adverse event

This refers to when a subject is discontinued for an adverse event. This includes cases when a subject is discontinued by request because of an adverse event and when a subject dies because of an adverse event and cannot continue in the study.

[2] Allowable range for the postoperative adjuvant chemotherapy schedule exceeded

This refers to when a subsequent course of postoperative adjuvant chemotherapy is not started within 43 days of the start of the most recent postoperative adjuvant chemotherapy (Day 1).

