# 12.6 Analysis of Efficacy

#### 12.6.1 Overall Information

This study is conducted to assess and characterize the clinical effect of ART-123 in preventing the onset of oxaliplatin-induced peripheral neuropathy and to explore appropriate efficacy endpoints. Thus, efficacy analyses will be performed primarily with descriptive statistics obtained by summarizing and graphing data from each evaluation time point.

The incidences of NCI-CTCAE Grade 1 or greater events will be evaluated with statistical tests and 95% confidence intervals as necessary in addition to descriptive statistics to allow intergroup comparison. The incidences of NCI-CTCAE Grade 1 or greater events with discontinuations and dropouts factored in will also be estimated.

The FAS will be used as the primary analysis population for evaluating efficacy. Similar analyses will be conducted as necessary with the PPS as a secondary analysis population to confirm the stability of the analysis results.

The significance level is set at 5% (two-sided), with a two-sided confidence interval and a confidence coefficient of 95%. Given the exploratory nature of the study, multiplicity will not be adjusted for.

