#### 12.6.2 Efficacy Endpoints

#### 12.6.2.1 NCI-CTCAE

For subjects found to have had one or more NCI-CTCAE Grade 1 or greater events during the study period, the incidence of NCI-CTCAE Grade 1 or greater events will be calculated by evaluation category, by course, and by treatment group. To provide reference data, differences will be calculated between the ART-123 1-dose and placebo groups and between the ART-123 3-dose and placebo groups. Moreover, survival analysis will be conducted with the occurrence of an NCI-CTCAE Grade 1 or

greater event during the study period considered to be an event, and Kaplan-Meier curves will be plotted with the incidence of events on the vertical axis and items (1) and (2) below on the horizontal axis

- (1) Observation period
- (2) Cumulative oxaliplatin dose

The occurrence of NCI-CTCAE Grade 2 and greater events will be analyzed similarly to NCI-CTCAE Grade 1 and greater events.

The number of subjects with events in each NCI-CTCAE grade will be tabulated by evaluation category, evaluation time point, and treatment group. As necessary, shift tables showing Day 1 of course 1 (baseline) and certain evaluation time points will be created for each treatment group.

- > Evaluation categories
  - Peripheral motor neuropathy
  - · Peripheral sensory neuropathy

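### Does counting subjects with missing neuropathy grades as events bias the incidence estimates by close to the planned precision?

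*Protocol*

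**What the plan says.** Section 12.4 gives the main rule for Grade 1 or greater status: "Consider subjects for whom these data are missing to have had an NCI-CTCAE Grade 1 or" greater event. It makes no distinction by reason. The next sentence plans a sensitivity analysis in which these subjects' grades stay missing. The section introduces its contents as the major rules and leaves details to data-handling criteria still to be written; section 12.2 leaves further detail to a SAP finalised before unblinding.

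Under section 12.6.2.1 the incidence "will be calculated by evaluation category, by course, and by treatment group". Kaplan-Meier curves follow, against observation time and against cumulative oxaliplatin dose. The section then says: "The occurrence of NCI-CTCAE Grade 2 and greater events will be analyzed similarly to NCI-CTCAE Grade 1 and greater events". Section 12.6.1 adds an incidence that takes discontinuations and dropouts into account, and section 12.6.2.7 allows, as necessary, further analyses of how missing data are handled.

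On size, section 12.1 reads: "To allow the estimation of the incidence of CIPN in each of the ART-123 1-dose, ART-123 3-dose, and placebo groups" with a precision of ±20%, "a target sample size of 25 per group for a total of 75 was selected". Section 9.6.1 names no primary endpoint, and section 12.6.1 calls the efficacy analysis primarily descriptive.

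**The concern.** The rule is blind to reason, and many exits listed in section 11.2.1 have nothing to do with neuropathy: the subject's own request, pregnancy, a sponsor decision, or a chemotherapy delay, of which the text says "This refers to when a subsequent course of postoperative adjuvant chemotherapy is not started within 43 days". Such a delay can follow from low neutrophil or platelet counts (section 8.3.2.1).

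If a withdrawn subject were scored as a case in every later course, the by-course incidence would rise with dropout alone and would resemble the cumulative-dose effect under study. If the Grade 2 analysis inherits the rule, the same happens there. The arms need not be affected equally. Section 10.2 flags bleeding and hypersensitivity, and withdrawals on active drug for those reasons would be scored as lost efficacy. The Kaplan-Meier analysis states no such imputation, so two analyses of the same subjects could disagree. At stake is whether the main incidence figures describe neuropathy or attrition.

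**Working it through.** **1. The plan's own figure.** Inputs: 25 per group and ±20% (section 12.1); two-sided 95% intervals (section 12.6.1). With the Wald interval at the least favourable p = 0.5, n = 1.96² × 0.25 / 0.20² = 24.01, rounded up to 25. The half-width at n = 25 is 1.96 × √(0.25/25) = 0.196. The sizing reproduces. The ±20% is stated for each group's CIPN incidence, not for each course.

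**2. Bias in one group.** Let p be the true incidence among subjects with missing status and m the missing fraction. If observed and missing subjects share the same p, the reported rate is p(1 − m) + m, so the bias is m(1 − p). If those who leave have more neuropathy than those who stay, the p in this formula is higher and the bias smaller.

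Bias in percentage points:

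| m | p = 0.95 | 0.85 | 0.60 | 0.50 | 0.40 | 0.30 | 0.10 |
|---|---|---|---|---|---|---|---|
| 10% | 0.5 | 1.5 | 4 | 5 | 6 | 7 | 9 |
| 20% | 1 | 3 | 8 | 10 | 12 | 14 | 18 |
| 30% | 1.5 | 4.5 | 12 | 15 | 18 | 21 | 27 |
| 40% | 2 | 6 | 16 | 20 | 24 | 28 | 36 |

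The protocol gives neither m nor a by-course p. Its one neuropathy rate is 85–95%, for acute symptoms (section 1.1.3). A bias of 18 points needs m = 0.18/(1 − p): 30% missing at p = 0.40, 36% at p = 0.50, 60% at p = 0.70. At p = 0.85 it would need 120%, which is impossible. The 85–95% rate need not hold in every course or for motor neuropathy, so it covers only the high-incidence case. Equally, nothing in the protocol supports 40–60%.

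**3. Bias in the difference.** With equal m in both arms, a true difference shrinks by the factor 1 − m: 20 points become 16 at m = 20% and 14 at m = 30%. With unequal m, take true rates of 30% on treatment and 50% on placebo:

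- 30% missing on treatment and 10% on placebo: 30 + 0.3 × 70 = 51% against 50 + 0.1 × 50 = 55%, a 4-point difference.
- 10% missing on treatment and 30% on placebo: 30 + 0.1 × 70 = 37% against 50 + 0.3 × 50 = 65%, a 28-point difference.

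**4. What counts as missing.** The rule speaks of subjects whose Grade 1 status is missing, not of single missed visits. Apart from the baseline grading, scheduled assessments record the worst condition since the preceding one (section 9.6.3.1), and the Day 1 grade of a later course is credited to the course before it (section 12.4). A missed Day 2 or Day 3 visit is therefore normally covered by the next grading.

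Withdrawal does not simply end grading either. A subject discontinued in the treatment period has an NCI-CTCAE evaluation that looks back to the last one (section 9.2.3). If that falls on or before Day 42 of the last course, the subject returns on Day 43 for another (sections 11.4.2 and 9.2.4.1). Stopping oxaliplatin stops the investigational product (section 8.1.4) but is not itself a criterion for leaving the study (section 11.2.1). The protocol does not state that courses never started after withdrawal count as missing.

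**5. Grade 2.** The imputation rule is headed and worded for Grade 1 or greater only. The sentence in section 12.6.2.1 on analysing Grade 2 similarly stands among incidence and survival methods and does not mention imputation.

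**The case for a change.** The strongest reply is that this is a main-analysis rule fixed in the protocol, not a detail left open, and that the protocol separates reasons elsewhere. For oxaliplatin discontinuation due to CIPN, section 12.6.2.6 censors other discontinuations. The reasons for stopping are recorded (sections 9.4 and 11.1), so a reason-specific rule would need no new data. The attenuation under equal missingness holds at any incidence, and a low-incidence cell, such as motor neuropathy or Grade 2 might be, could show a large bias: 5 of 25 missing at an assumed p = 0.10 gives 0.20 × 0.90 = 18 points.

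Much of this stands as arithmetic. The rule is reason-blind, and it is not conservative in every case, as the second example under unequal missingness shows. But the reader will not be left with this analysis alone. The result with grades left missing is already required, as are the dropout-adjusted incidence and the Kaplan-Meier curves. Making the assessed-only analysis the main one would largely exchange two planned results, adding selective imputation for CIPN-related exits. It brings a bias of its own when subjects leave because of neuropathy; imputing an event only for recorded CIPN or lack of efficacy repairs part of that. Divergence between imputed and censored results is what such comparisons are meant to reveal.

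**Conclusion.** The concern does not hold. The formula and its worked values are correct, but a bias close to the planned precision needs a low or moderate incidence together with substantial missingness, and the protocol states neither. At 20–30% missing, an assumed range, the bias is 1 to 4.5 points if incidence is near the 85–95% cited for acute symptoms, and 8 to 18 points if it is 40–60%. The more serious reading, with withdrawn subjects scored as cases in every later course and at Grade 2, is not in the text.

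Reasonable statisticians differ between worst-case imputation and an assessed-only analysis with selective imputation. In an exploratory, mainly descriptive trial without a primary endpoint, with the alternative analysis already planned, the choice is acceptable. What the protocol leaves unsaid is the unit of the rule (visit, course or whole study) and whether it reaches Grade 2. Those details belong to the data-handling criteria and the SAP, which are not at hand.

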# 12.5 Analysis of Demographic Variables and Other Baseline Characteristics

Summary statistics will be calculated and categorical tabulations will be performed for demographic variables and other baseline characteristics in the FAS on a by-group basis.

# 12.6 Analysis of Efficacy

#### 12.6.1 Overall Information

This study is conducted to assess and characterize the clinical effect of ART-123 in preventing the onset of oxaliplatin-induced peripheral neuropathy and to explore appropriate efficacy endpoints. Thus, efficacy analyses will be performed primarily with descriptive statistics obtained by summarizing and graphing data from each evaluation time point.

The incidences of NCI-CTCAE Grade 1 or greater events will be evaluated with statistical tests and 95% confidence intervals as necessary in addition to descriptive statistics to allow intergroup comparison. The incidences of NCI-CTCAE Grade 1 or greater events with discontinuations and dropouts factored in will also be estimated.

The FAS will be used as the primary analysis population for evaluating efficacy. Similar analyses will be conducted as necessary with the PPS as a secondary analysis population to confirm the stability of the analysis results.

The significance level is set at 5% (two-sided), with a two-sided confidence interval and a confidence coefficient of 95%. Given the exploratory nature of the study, multiplicity will not be adjusted for.

#### 12.6.2 Efficacy Endpoints

#### 12.6.2.1 NCI-CTCAE

For subjects found to have had one or more NCI-CTCAE Grade 1 or greater events during the study period, the incidence of NCI-CTCAE Grade 1 or greater events will be calculated by evaluation category, by course, and by treatment group. To provide reference data, differences will be calculated between the ART-123 1-dose and placebo groups and between the ART-123 3-dose and placebo groups. Moreover, survival analysis will be conducted with the occurrence of an NCI-CTCAE Grade 1 or

greater event during the study period considered to be an event, and Kaplan-Meier curves will be plotted with the incidence of events on the vertical axis and items (1) and (2) below on the horizontal axis

- (1) Observation period
- (2) Cumulative oxaliplatin dose

The occurrence of NCI-CTCAE Grade 2 and greater events will be analyzed similarly to NCI-CTCAE Grade 1 and greater events.

The number of subjects with events in each NCI-CTCAE grade will be tabulated by evaluation category, evaluation time point, and treatment group. As necessary, shift tables showing Day 1 of course 1 (baseline) and certain evaluation time points will be created for each treatment group.

- > Evaluation categories
  - Peripheral motor neuropathy
  - · Peripheral sensory neuropathy

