## 1.1.3 Oxaliplatin-induced Peripheral Neuropathy

Oxaliplatin-induced peripheral neuropathy takes the forms of acute peripheral neuropathy, which appears just after to several days after oxaliplatin administration, and chronic peripheral neuropathy, which appears later over the course of oxaliplatin treatment. Temporary numbness and abnormal sensations in the limbs and mouth, one manifestation of acute peripheral neuropathy, affect almost everyone (85% to 95%) treated with oxaliplatin. Manifestations of chronic peripheral neuropathy include persistent numbness and abnormal sensations of the limbs, fine-motor impairments such as difficulty buttoning clothing, and movement disorders such as difficulty walking. The risk of these conditions increases as the cumulative dose of oxaliplatin increases. These conditions, moreover, substantially reduce patient quality of life (QOL). The modification and discontinuation of chemotherapy caused by chronic peripheral neuropathy is particularly clinically significant .

Although the specific mechanism of the onset of oxaliplatin-induced peripheral neuropathy remains uncharacterized, chronic peripheral neuropathy is attributed to axonal degeneration resulting from nerve cell body damage. Because damaged nerves require a long time for repair, symptoms may persist for several months or years after the end of oxaliplatin treatment. Preventing the onset of oxaliplatin-induced peripheral neuropathy is therefore important.

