## 3.3 Rationale for Inclusion and Exclusion Criteria

## 3.3.1 Rationale for Inclusion Criteria

- [1] Subjects must be at least 20 years old to be sufficiently competent to give consent. An upper age limit of 79 years was set out of concern for subject safety.
- [2] The sex of the subjects is not limited because sex is not thought to affect the evaluation of efficacy or safety in the study.
- [3] The hospitalization status of the subjects is not limited because this is not thought to affect the evaluation of efficacy or safety in the study.
- [4] and [5] The study will be in patients with colorectal cancer following radical resection, who have a better prognosis than patients with unresectable, advanced, or recurrent colorectal cancer. The study will be in patients with pStage II or III colon cancer following resection because the Guidelines for the Treatment of Colorectal Cancer, in the section on chemotherapy eligibility, requires Stage II colorectal cancer with a high risk of recurrence or Stage III colorectal cancer for postoperative adjuvant chemotherapy, and patients with Stage II and III colon cancer are indicated for postoperative adjuvant chemotherapy in the package insert of oxaliplatin.
- [6] This criterion was established to select relatively healthy subjects.
- [7] This criterion was established out of concern for subject safety.
- [8] The efficacy of Recomodulin will be investigated on CIPN induced by oxaliplatin, which frequently causes this condition. The oxaliplatin-containing postoperative adjuvant chemotherapy regimens recommended in the Guidelines for the Treatment of Colorectal Cancer are FOLFOX and CapeOX. FOLFOX compliance is readily determinable because the regimen is administered under the control

of healthcare professionals, which makes the regimen ideal for this first study to evaluate the efficacy of Recomodulin in CIPN. The standard FOLFOX regimen mFOLFOX6 was selected. The standard mFOLFOX6 treatment duration of 6 months (12 courses) was selected to allow evaluation of the efficacy of Recomodulin in oxaliplatin-induced chronic neuropathy.

[9] This criterion was established to ensure that the study is ethically consistent.

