# 9.2.2.3 Day 8 of Course 1\*1

- Efficacy endpoint survey
  - FACT/GOG-NTX-12
  - NRS (pain)
  - \*1 No office visit required. The survey may be performed when the subject is at home or elsewhere.

# 9.2.2.4 Day 15 (permitted window, +7 days)\*1 and Day 29 (permitted window, +7 days)\*1 of Course 1

- · Concomitant medications/therapies survey
- · Adverse events survey
- · Investigational product administration status survey
- · Postoperative adjuvant chemotherapy administration status survey
- Efficacy endpoint survey
  - NCI-CTCAE
    - i) The worst condition noted between the preceding evaluation (excluding any unscheduled evaluation) and the day of evaluation
    - ii) Condition at the time of evaluation
  - DEB-NTC
  - FACT/GOG-NTX-12
  - NRS (pain)
  - \*1 To be performed only in the event of postponement of the administration of all drugs for postoperative adjuvant chemotherapy

# 9.2.2.5 Day 1 of Courses 2 to 12

- > Before investigational product administration
  - Concomitant medications/therapies survey
  - · Adverse events survey
  - Efficacy endpoints survey
    - NCI-CTCAE
      - i) The worst condition noted between the preceding evaluation (excluding any unscheduled evaluation) and the day of evaluation
      - ii) Condition at the time of evaluation
    - DEB-NTC

- FACT/GOG-NTX-12
- FACT-G\*1
- NRS (pain)
- Pregnancy test (only subjects for whom the test is required)\*2
- Vital sign measurement
- Laboratory tests (blood/urine)\*3
- Weighing of subject to determine investigational product dose\*3
- > Investigational product administration and administration status survey
- ➤ After investigational product administration
  - Postoperative adjuvant chemotherapy administration and administration status survey
  - · Adverse events survey
    - \*1 To be performed only in Courses 5 and 9
    - \*2 To be performed only in Course 2; may be determined on the day before Day 1
    - \*3 May be determined on the day before Day 1

# 9.2.2.6 Days 2 and 3 of Courses 2 to 12

- ➤ Before investigational product administration
  - Concomitant medications/therapies survey
  - Adverse events survey
  - Efficacy endpoint survey
    - NCI-CTCAE: The worst condition noted between the preceding evaluation (excluding any unscheduled evaluation) and the day of evaluation
- > Investigational product administration and administration status survey
- > Fluorouracil continuous intravenous infusion status survey
- > After investigational product administration

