# 9.6.3 Evaluation Methods

# 9.6.3.1 NCI-CTCAE Peripheral Motor Neuropathy, Peripheral Sensory Neuropathy (CIPN only)

The investigator or subinvestigator will evaluate neuropathy as follows:

- > Assessment time points
  - Days 1, 2, 3, 15\*1, and 29\*1 of courses 1 to 11
  - Days 1, 2, 3, and 15 of course 12
  - At Study completion
  - · At Discontinuation in the Treatment Period
  - At unscheduled CIPN evaluations
    - \*1 To be performed only in the event of postponement of the administration of all drugs for postoperative adjuvant chemotherapy

- > Information to be determined and evaluated
  - Date and time point of evaluation (before investigational product administration/after investigational product administration/not applicable)
  - Evaluate the grade on a 6-step scale (none, Grade 1 to 5) for each of the evaluation classifications (peripheral motor neuropathy, peripheral sensory neuropathy) based on the NCI-CTCAE grade classification system provided in Appendix 3
  - Assess the condition at the time of evaluation on Day 1 of course 1
  - On Days 15 and 29 of courses 1 to 11 and Day 1 of courses 2 to 12, assess the worst condition noted between the preceding evaluation (excluding any unscheduled evaluation) and the day of evaluation and the condition at the time of evaluation
  - On days of evaluation other than Day 1 and Days 15 and 29 of courses 1 through 11, assess the worst condition noted between the preceding evaluation (excluding any unscheduled evaluation) and the day of evaluation. At unscheduled CIPN evaluations, assess the worst condition noted between the preceding evaluation and the day of evaluation

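### Study-long Grade 1 or greater sensory incidence and its Kaplan-Meier curve would sit near ceiling from acute episodes, leaving little room to show an effect confined to chronic neuropathy

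*Protocol*

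**What the plan says.** Protocol 1.1.3 describes two forms of oxaliplatin neuropathy. The acute form, "which appears just after to several days after oxaliplatin administration", is temporary, and its sensory symptoms "affect almost everyone (85% to 95%) treated with oxaliplatin". The chronic form comes later and rises with cumulative dose. The chemotherapy changes that it causes are singled out as clinically important.

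Section 3.3.1, item [8], explains that the 12-course duration "was selected to allow evaluation of the efficacy of Recomodulin in oxaliplatin-induced chronic neuropathy".

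Section 12.6.2.1 states that "survival analysis will be conducted with the occurrence of an NCI-CTCAE Grade 1 or" greater event during the study period as the event. Curves are drawn against observation time and against cumulative oxaliplatin dose. Incidence is given by motor or sensory category, by course and by group, with differences from placebo as reference data. Grade 2 or greater is handled in the same way. Section 12.6.1 names Grade 1 or greater incidence as the outcome for tests and 95% confidence intervals where needed.

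Two kinds of grade are collected:

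- Days 2 and 3 of every course (9.2.2.2, 9.2.2.6): "NCI-CTCAE: The worst condition noted between the preceding evaluation (excluding any unscheduled evaluation) and the day of evaluation". No other grade is taken on those days.
- Day 1 of courses 2 to 12, and Days 15 and 29 when all drugs are postponed (9.2.2.4, 9.2.2.5, 9.2.2.8): the worst grade, and also "ii) Condition at the time of evaluation".

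Section 12.4 counts Days 2, 3, 15 and 29 within their own course and treats the Day 1 "grades as those from the immediately preceding course". Subjects with missing Grade 1 status count as having had an event. Section 12 does not say which of the two Day 1 grades enters the analyses.

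**The concern.** Days 2 and 3 lie inside the acute window that 1.1.3 describes. The event in 12.6.2.1 has no persistence requirement and does not separate acute from chronic symptoms. A single transient episode after any dose therefore ends a subject's event-free time, and whatever happens later over the remaining courses adds nothing to that summary.

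If nearly every subject becomes an event through acute symptoms, the study-long sensory summary mostly records acute onset. A drug that prevented much of the chronic neuropathy but left acute symptoms alone would give much the same high incidence in all three arms. Someone who reads that result as the trial's answer on prevention could conclude that there is no effect on the form that the 12 courses were chosen to study. The rule that counts missing data as events pushes incidence further towards the ceiling.

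**Working it through.** **Plan's own figure.** Section 12.1 gives 25 per group for a precision of ±20 points. With a normal-approximation 95% interval at p = 0.5 (method assumed, as none is stated), n = 1.96² × 0.25 / 0.20² = 24.01, hence 25. The half-width at n = 25 is 19.6 points. The figure reproduces.

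**Inputs from the protocol.** Acute rate A = 85% to 95% (1.1.3); 25 per group (12.1); two-sided 5% level (12.6.1).

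**Assumed.** Acute symptoms are graded 1 or greater. The chronic rate C is 60% on placebo and 30% on ART-123 (the protocol gives no chronic rate). ART-123 does not change A. Acute and chronic neuropathy occur independently.

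**Step 1: subjects left event-free by acute symptoms alone.** 25 × (1 − 0.85) = 3.75 and 25 × (1 − 0.95) = 1.25 per group.

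**Step 2: how a chronic-only effect appears.** Ever Grade 1 or greater = 1 − (1 − A)(1 − C), so the visible difference is (1 − A) × 0.30. Power is for n = 25 per arm.

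| A | Placebo | ART-123 | Difference | Power, normal approx. | Power, Fisher |
|---|---|---|---|---|---|
| 85% | 94.0% | 89.5% | 4.5 points | 8.3% | 1.3% |
| 90% | 96.0% | 93.0% | 3.0 points | 6.7% | 0.3% |
| 95% | 98.0% | 96.5% | 1.5 points | 5.1% | 0.0% |

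If every chronic case also had an acute episode, the difference would be 0. On an outcome free of acute symptoms, the same effect is 30 points, with 57% power (Fisher 51%).

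**Step 3: other chronic rates.** For 50% against 25%, the differences are 3.8, 2.5 and 1.3 points, against 25 points without acute symptoms. For 80% against 40%, they are 6, 4 and 2 points, against 40.

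**Step 4: upper bound.** Suppose that chronic neuropathy is abolished and every placebo subject has an event. The gap is then at most 1 − A: 15, 10 or 5 points. Against 25/25 on placebo, a Fisher test at 5% needs 19/25 or fewer (p = 0.022), a 24-point gap. The chance of 19 or fewer when the true rate is 85%, 90% or 95% is 16%, 3% and 0.1%.

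**Step 5: which analyses this covers.** The 85% to 95% is the share of patients ever affected by sensory-type symptoms. The protocol gives no per-course acute rate, no acute motor rate and no acute rate at Grade 2 or greater. The arithmetic therefore applies to the study-long sensory Grade 1 summary and its curve only. By-course sensory incidence also mixes acute with chronic symptoms, but how close it comes to the ceiling cannot be computed from this document.

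**The case against.** The case on the other side has real weight.

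- **Other curves exist.** Section 12.6.2.6 plans Kaplan-Meier curves, on both axes, for oxaliplatin discontinuation, and for discontinuation, suspension or reduction, due to CIPN. Table 8.3-5 ties reduction and suspension mainly to the Day 1 grade on the day of evaluation. A reader might infer that 12.6.2.1 holds the only curves in the plan. That is not so. These curves do bear on lasting neuropathy, but they record changes to chemotherapy and not the onset of persistent neuropathy.
- **Time-point summaries exist.** Every CTCAE grade is tabulated by visit, and DEB-NTC and FACT/GOG-NTX-12 are summarised by visit. For completers, the study-completion grade covers the period from Day 15 of course 12, largely past the acute window. This limits the harm, but it gives no incidence, difference or curve for persistent onset.
- **The objective is general.** Section 2 speaks of onset of oxaliplatin-induced neuropathy, without limiting it to the chronic form. An effect on acute symptoms could show in the Grade 1 analyses. This stands: the limitation concerns an effect confined to chronic neuropathy.
- **The study is exploratory.** No endpoint is primary, tests are used only as needed, and no decision rests on Grade 1 alone. This lowers the stakes. However, 12.6.1 gives exploring suitable endpoints as a purpose, and the Grade 1 summary would be a poor guide to chronic prevention.
- **Details may be in the SAP.** The choice of Day 1 grade may be settled there. The protocol itself fixes the event, though, and acute episodes enter through Days 2 and 3 whichever Day 1 grade is used.

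A reader might also infer that every CTCAE analysis is saturated, or that the trial cannot show an effect on chronic neuropathy at all. The documents support neither inference: the needed motor, by-course and Grade 2 rates are absent, and the analyses listed above remain available.

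**Conclusion.** The point holds for the study-long Grade 1 or greater sensory incidence and its Kaplan-Meier curve. On the protocol's own acute rate, about 1 to 4 of 25 subjects per group would be event-free. An assumed 30-point reduction in chronic neuropathy alone would shrink to 1.5 to 4.5 points, and even complete prevention of chronic neuropathy could show at most 5 to 15 points.

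This rests on acute symptoms being graded 1 or greater (nothing shown excludes them, but the grading appendix is not available) and on a drug effect limited to chronic neuropathy. The 1.5 to 4.5 points also need the assumed chronic rates and independence; the upper bound does not.

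By-course sensory incidence is contaminated but not shown to be saturated. Nothing is shown about saturation of the motor or Grade 2 or greater analyses. The change should be made, because a null Grade 1 result could be misread and the data needed are mostly collected already.

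**What to change.** Before unblinding, add a persistent-CIPN analysis to 12.6.2.1: by-course incidence, differences from placebo and both Kaplan-Meier curves, for Grade 1 or greater and for Grade 2 or greater.

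- **Courses 1 to 11.** Use the pre-dose current-condition grade from Day 1 of the next course (courses 2 to 12), assigned to the preceding course. Where all drugs were postponed, use that course's Day 15 current-condition record.
- **Course 12, and a discontinuing subject's last course.** Use the study-completion (Day 43) grade. Day 15 of course 12, treatment discontinuation and study completion record only the worst grade, so there is no current-condition reading at those visits. For completers, the Day 43 grade is the worst since Day 15 and so largely free of acute episodes. For discontinuing subjects, that is true only if the preceding evaluation fell after the acute window; state this as a limitation.
- **Wording.** State which Day 1 grade feeds each analysis, and that the worst-grade analyses describe acute plus chronic CIPN.

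The cost is protocol or SAP wording and one more set of exploratory tables and curves, with no new visit or form. The drawback is that the last-course reading is taken later, and on a different basis, than in the other courses.
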